iii. Adverse event of muscle symptoms (e.g., myalgia, pain, or weakness) or elevated creatine kinase:

A sample will be collected for assessment of CK within 48-72 hours, and CK assessment will be repeated if needed (refer to [Appendix 5](#)). At Weeks 12 and 24, the creatine kinase (CK) level will be compared to the subject's baseline level.

- If CK level is $\leq 3x$ baseline, subject will continue on aldafermin and over-encapsulated rosuvastatin.
- If CK level is $> 3x$ baseline, CK will be repeated within 48 - 72 hours and aldafermin and rosuvastatin will be held:
 - If CK is $\leq 3x$ baseline, subject can re-start on aldafermin and rosuvastatin based on the investigator's judgement.
 - If CK is $> 3x$ and $< 5x$ baseline, repeat CK levels within 48 - 72 hours while aldafermin and rosuvastatin on hold.
 - If CK is $\geq 5x$ baseline, aldafermin and rosuvastatin will be discontinued.

Upon repeat testing for subjects previously with CK $> 3x$ but $< 5x$ baseline:

- If CK is $\leq 3x$ baseline, subject can re-start on aldafermin and rosuvastatin based on the investigator's judgement.
- If CK level is $> 3x$ baseline, subject will discontinue aldafermin and rosuvastatin.

iv. Laboratory value(s) indicative of DILI:

- a) Elevation of AST or ALT $> 2x$ above subject-specific baseline value (calculated using the average of the Day -42, Day -28 and the Day 1 values) and total bilirubin $> 1.5 \times$ subject-specific baseline value, repeat testing of ALT, AST, and bilirubin must be performed within 48 - 72 hours. If there are persistent elevations (AST or ALT $> 2x$ baseline or TBL $> 1.5x$ baseline values) upon repeat testing, then close observation (testing and physical examination 2 - 3 times per week) should be implemented and discontinuation of aldafermin and rosuvastatin should be considered (see b [below](#)).
- b) A decision to discontinue or temporarily interrupt the study drug will be considered based on factors that include how much higher than baseline ALT and AST were relative to the upper limit of normal (ULN) and how much the on study ALT and AST levels have increased relative to baseline, in addition to whether there is concomitant elevation of bilirubin or INR. Aldafermin and rosuvastatin will be discontinued or temporarily interrupted as follows:
 - If baseline measurements (BLM) were $< 2x$ ULN, discontinue if ALT or AST increases to $> 5x$ BLM
 - If BLM $\geq 2x$ ULN but $< 5x$ ULN, discontinue if ALT or AST increases to $> 3x$ BLM

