^c During screening, sites will complete; i) AUDIT-C alcohol consumption questionnaire and, ii) document subject- reported alcohol consumption to confirm whether amounts are within protocol defined limits (refer to exclusion criterion #19)

^d Screening Day -28 MRI-PDFF (includes [REDACTED]) will serve as baseline for efficacy endpoint analysis. The Screening MRI result is valid for up to 8 weeks and may be used for a subject who is re-screened within that time frame. [REDACTED]

^e All subjects are required to have a liver biopsy result at Screening and additional liver biopsy at Week 24. A Screening liver biopsy will be performed only in subjects who do not have a historical biopsy available within 6 months of Screening.

^f Adverse events will be monitored and recorded from subject signing informed consent through follow-up.

^g Serum chemistry will include ALT, AST, ALP, bicarbonate, bilirubin (direct and total), BUN, calcium, chloride, creatinine, CK, GGT, glucose, HDL, LDL, lipase, phosphate, potassium, proteins (albumin, total protein), sodium, total cholesterol, and TG. Lab results for ALT, AST, total cholesterol, LDL, HDL, and triglycerides are blinded to the site and sponsor from Week 2 onward.

^h Creatine Kinase will be collected at Day -42, Day 1 and Week 12, and Week 24.

ⁱ A serum pregnancy test will be performed on all female subjects of childbearing potential at Day -42, -28 Screening visits and Day 1 (pre-dose). A urine pregnancy test will be performed on all female subjects of childbearing potential at Weeks 4, 12, 24, and 30. If the urine pregnancy test is positive, a serum pregnancy test will be performed to confirm

results.

^j Urine drug and alcohol screens may be repeated during treatment for subjects suspected of excessive alcohol intake or to rule out association with a safety event

^k C4 and bile acid testing will be collected at Day 1 and Weeks 2, 4, 8, 12, 18, 24, 25 and 30. In addition, for subjects participating in the optional PK sub-study, additional C4 will be tested at the same timepoints as the PK blood sample collections: Day 1 and Week 24 at pre-dose, and post-dose at 0.5, 1, 2, 4, 6, 8, 12, and 24 hours.

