#### 2.2 Data Conventions

The following data conventions will be used for all analyses described in this SAP.

- All subject-level data will be provided in data listings, unless stated otherwise.
- Study day will be calculated as:
  - o visit date first dose date, for screening visits;
  - o visit date first dose date + 1, for post-baseline/treatment visits.
- Baseline value will be defined as the last available, valid, non-missing assessment reported before the start of first study drug administration. The randomization date (and time, if available) will be used if the study drug start date is missing or not available for any reason.
- Change from baseline (change) is calculated as follow-up baseline. Percent (or relative) change from baseline (percent/relative change) is calculated as 100 × (change from baseline/baseline).
- Descriptive statistics including the number of non-missing observations (n), arithmetic mean (mean), standard deviation (SD), median, minimum (min), and maximum (max) will be presented for continuous endpoints. Frequency and percentage distribution will be presented for categorical endpoints. Kaplan-Meier estimates will be presented for time-to-event endpoints if applicable.
- Continuous endpoints will be analyzed using an analysis of variance (ANOVA) or analysis of covariance (ANCOVA) model. Ordinal categorical endpoints will be analyzed using a Wilcoxon rank-sum test. Nominal categorical endpoints will be analyzed using a Pearson's Chi-square test or Cochran-Mantel-Haenszel (CMH) test (A Fisher's exact test will be used if ≥ 25% of the cells have expected counts < 5). Time-to-event endpoints will be analyzed using a (stratified) log-rank test and Cox's proportional hazards model.

- Type III sums of squares will be used for all ANOVA and ANCOVA models.

- The level of statistical significance used for all statistical tests will be 0.05, unless stated otherwise. Statistical hypotheses for the primary efficacy analyses and the associated sensitivity analyses will be tested for statistical significance with two-sided alternatives, and one-sided alternatives will be used for all secondary and other efficacy analyses. All confidence intervals (CIs) will be two-sided, unless stated otherwise.
- Data from unscheduled visits will be presented in data listings, but will not be used for statistical analysis/summaries.

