#### 2.3 Visit Windows

No analysis visit windows will be defined for this study, i.e., the nominal visits /time-points will be used for all statistical summaries/analyses.

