## 6.3 Clinical Laboratory Evaluations

Clinical laboratory evaluations include biochemistry, hematology and urinalysis. Actual values and change from baseline values of continuous laboratory tests will be summarized by treatment group for each visit. For categorical lab tests, frequency and percentage distribution will be presented by treatment group for each visit.

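### Off-schedule CK and liver-test values required by Protocol 8.3 cannot reach any between-arm laboratory table, because SAP 2.2 confines unscheduled data to listings and SAP 6.3 plans only by-visit summaries

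*SAP*

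**What the plan says.** SAP 2.2 sets the rule: "Data from unscheduled visits will be presented in data listings, but will not be used for statistical analysis/summaries". The section opens by giving its scope: "The following data conventions will be used for all analyses described in this SAP". Safety is therefore covered. SAP 2.3 defines no analysis windows and says that "the nominal visits /time-points will be used for all statistical summaries/analyses", so an off-schedule draw cannot be assigned to a neighbouring visit.

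For laboratory data, SAP 6.3 plans this: "Actual values and change from baseline values of continuous laboratory tests will be summarized by treatment group for each visit". Categorical tests get frequencies by visit. The section has no worst post-baseline value, shift or threshold table, and no unredacted safety section lifts the rule in 2.2.

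Protocol 8.3 sets out what happens between visits:
- After a muscle-symptom event or raised CK: "A sample will be collected for assessment of CK within 48-72 hours, and CK assessment will be repeated if needed".
- If CK exceeds 3 times baseline: "CK will be repeated within 48 - 72 hours and aldafermin and rosuvastatin will be held". The next step depends on the repeat.
- For suspected drug-induced liver injury: "repeat testing of ALT, AST, and bilirubin must be performed within 48 - 72 hours". Close observation then means liver tests two or three times a week.
- For other suspected statin-related events, when the next visit is 2 weeks or more away, laboratory tests are repeated at a visit the protocol itself calls unscheduled.

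Footnote h of Protocol Table 4 gives the routine CK schedule: "Creatine Kinase will be collected at Day -42, Day 1 and Week 12, and Week 24".

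**The concern.** The protocol puts its confirmatory liver and muscle measurements on draws outside the visit schedule, and the SAP keeps draws of that kind out of every summary. A reader of the study report could compare arms on scheduled laboratory values only. The values that settled whether a subject restarted, stayed on hold or stopped would have to be pieced together from listings.

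This matters because safety and tolerability, as a function of dose, are among the primary objectives (Protocol 6.1). Protocol 5.4 also says that rosuvastatin co-administration is being studied for safety and tolerability. Liver enzymes and CK are the laboratory measures on which Protocol 8.3 bases its specific actions for these two drugs.

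**Working it through.** The plan gives no figure to reproduce. The check is a reading of the rules together, a count of draws, and an illustration.

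**1. Do the Protocol 8.3 draws count as unscheduled?** Post-dose chemistry is scheduled at Weeks 2, 4, 8, 12, 18, 24, 25 and 30, which is 8 visits (Protocol Table 4). From Day 1 to Week 24 the gaps are 2, 2, 4, 4, 6 and 6 weeks. A repeat at 48-72 hours, or testing two or three times a week, will nearly always fall inside a gap. Protocol 8.3 does not label these repeats unscheduled; that follows from the calendar. Only the statin-event repeat uses the word. A repeat can occasionally coincide with a visit.

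**2. What stays in the tables?** SAP 2.2 includes the minimum and maximum among its descriptive statistics. An elevation first found at a scheduled visit therefore shows in that visit's maximum for the arm. What drops out is a first draw prompted by symptoms between visits, and every off-schedule repeat, including any that is higher than the trigger value.

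**3. How many draws can be excluded?** Close observation across one 6-week gap gives 6 × 2 = 12 to 6 × 3 = 18 draws. Protocol 8.3 lets the frequency fall once values stabilise, or once drug is stopped and the subject is asymptomatic, so this is an upper range.

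**4. How often would a scheduled draw fall inside an elevation?** Assume onset uniform over days 0 to 168 and an elevation lasting D days. A draw on day d falls inside if onset lies between d − D and d. The share is the combined length of these intervals within 0 to 168, divided by 168.

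- Chemistry draws fall on days 14, 28, 56, 84, 126, 168, 175 and 210. For these values of D, the last two add nothing beyond the day-168 interval.
- CK draws, read as Weeks 12 and 24 only, fall on days 84 and 168.

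| Assumed D | Chemistry | CK |
|---|---|---|
| 3 days | 6 × 3 / 168 = 11% | 2 × 3 / 168 = 4% |
| 7 days | 6 × 7 / 168 = 25% | 2 × 7 / 168 = 8% |
| 14 days | 6 × 14 / 168 = 50% | 2 × 14 / 168 = 17% |
| 28 days | 140 / 168 = 83% | 2 × 28 / 168 = 33% |

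At 28 days the first two chemistry intervals overlap: together they cover days 0 to 28, and the next four add 28 days each, so 5 × 28 = 140. A simulation gave the same percentages. The durations are assumptions, and early-withdrawal visits, which also carry chemistry, are ignored.

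**5. Is the CK column secure?** No. Table 4 footnote g and Protocol 9.4.9 list CK within serum chemistry, which is drawn at every visit. Footnote h and a later sentence in 9.4.9 limit CK to four time points, two of them post-dose. If CK runs with every panel, the chemistry column applies to CK too.

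**The case against.** The strongest reply is that the safety signal has another route. The primary safety endpoint is adverse events, not laboratory values. Protocol 11.1 counts clinically relevant laboratory changes as adverse events. SAP 6.2 tabulates treatment-emergent events by arm, by CTCAE grade, by relationship to each drug, and by whether they led to withdrawal. Nothing there limits events to scheduled visits, and at about 38 subjects per arm the listings can be read.

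Much of this stands: the events are not lost from the report. It does not close the gap, for two reasons. The adverse event tables carry terms and grades, so they do not count subjects crossing the Protocol 8.3 multiples of baseline. And Table 4 footnote g blinds ALT and AST results to site and sponsor from Week 2 onward, so complete investigator reporting of those two analytes cannot be assumed.

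A reader might also infer more than the documents support:
- That peak values in general will be missing. They will not; the maximum at each scheduled visit is reported.
- That the tables omit the values that led to drug being held. For a CK found high at Week 12 or 24, the trigger value stays in, and the excluded repeat is the one taken during the hold.
- That essentially every symptom-driven CK is excluded. That depends on the unresolved CK schedule and on whether a draw coincides with a visit.
- That the comparison is biased towards no difference. This is plausible if events are commoner on active drug, but nothing in the documents fixes its direction or size.

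**Conclusion.** The point holds in a limited form. Followed as written, SAP 2.2, 2.3 and 6.3 keep CK, ALT, AST and bilirubin values from off-schedule Protocol 8.3 draws out of every between-arm laboratory table, and no table counts subjects crossing the Protocol 8.3 thresholds. This is a stated rule with a definite consequence, not a missing detail.

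The effect is confined to laboratory safety reporting in a descriptive analysis. The primary efficacy analysis and the adverse event tables are untouched. Under the illustration, the gap is large for short elevations and modest for chemistry once they last about four weeks. The percentages rest on uniform onset and assumed durations, and the CK figures also on the Weeks 12 and 24 reading. The plan should be changed, and the change is a cheap improvement.

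**What to change.** Keep the by-visit summaries on scheduled data, and make these changes before database lock:
- In SAP 2.2, exempt safety laboratory data from the rule on unscheduled visits.
- In SAP 6.3, add tables by arm of worst post-baseline value and shift from baseline for ALT, AST, total bilirubin, INR and CK, using scheduled and unscheduled values together.
- In SAP 6.3, add counts by arm of subjects meeting each CK and liver threshold already written in Protocol 8.3. No clinical rule changes.
- State the baseline for each table. Protocol 8.3 averages the Day -42, Day -28 and Day 1 values for the liver rule; SAP 2.2 takes the last pre-dose value. Use the average for the liver thresholds and the SAP definition otherwise.
- State how local-laboratory results are included. Protocol 8.3 allows local testing for subjects in remote areas and says only that results go to the site, so their presence in the database needs confirming.
- Reconcile the two statements of the CK schedule.

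Both SAP changes are needed: lifting the exclusion alone creates no per-subject table. The cost is a few extra tables, a second baseline derivation and a rule for local results. Subjects tested more often have more chance of a high maximum. A footnote should say so; it discloses that imbalance but does not remove it.

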#### 2.3 Visit Windows

No analysis visit windows will be defined for this study, i.e., the nominal visits /time-points will be used for all statistical summaries/analyses.

## 3. Disposition and Exit Status

## 3.1 Disposition and Exit Status

Subject disposition will be summarized by treatment group and overall using the ITT analysis set. The number and percent of subjects screened, enrolled, completed, and prematurely discontinued, along with the primary reason for the discontinuation (per study eCRF specifications) will be presented.

#### 3.2 Protocol Deviations

Subject data will be examined prior to database lock or unblinding for evidence of protocol deviations in order to identify subjects with protocol violations that could exclude such subjects from the PP analysis set. Classification of possible protocol deviations will be reviewed and approved by the study team based on predefined criteria. Protocol deviations will be provided in data listings.

## 4. Demographics and Other Baseline Characteristics

## 4.1 Demographics

Demographics will be summarized with descriptive statistics by treatment group and overall for each analysis set. These variables include age (years), sex (Male or Female), race (Asian, Black, White, etc.), ethnicity (Hispanic/Latino, Not Hispanic/Latino, Not Reported, or Unknown), body weight (kg), height (cm), body mass index (BMI, kg/m²) and waist circumference (cm) at Screening.

#### 4.2 Disease Characteristics

Baseline disease characteristics will be summarized with descriptive statistics by treatment group and overall for each analysis set. These variables include NAS score, fibrosis stage (2 or 3), type 2 diabetes status (Yes/No), LFC (%) by MRI PDFF, ALT, AST, cholesterol, HDL-C, LDL-C, triglycerides, Pro-C3, ELF, and C4.

#### 4.3 Prior and Concomitant Medications

Medications taken at least once within 42 days prior to Screening visit and during the study period as well as the reason for use will be recorded in the source documents and the eCRFs.

- **Prior medications**: are defined as any medication which is administered any time prior to the study treatment starting time, regardless of when the medication stops.
- Concomitant medications: are defined as any medication which is administered any time after the study treatment starting time, regardless of when the medication starts or stops.

A given medication may be classified both as a prior medication and as a concomitant medication.

All medications will be coded using the World Health Organization Drug Dictionary Global (WHODrug Global, B3, March 2018). The number and percentage of subjects taking prior/concomitant medications will be summarized by the drug class from the Anatomical-Therapeutic-Chemical (ATC) classification level 4 and WHODrug Global drug name (preferred name) for each treatment group and overall using the ITT analysis set. For these summaries, subjects who take the same medication (i.e., the same preferred name) more than once will be counted only once for that medication.

# 4.4 Medical History and Concurrent Procedures

Medical history will be coded using MedDRA version 23.0. The number and percentage of subjects with medical history will be summarized by primary SOC and preferred term by

treatment group and overall using the ITT analysis set. Surgical procedures recorded for the corresponding events and concurrent procedures will be provided in the data listings.

## 5. Efficacy Analyses

All efficacy endpoints will be summarized with descriptive statistics by treatment group (0.3 mg Aldafermin, 1 mg Aldafermin, 3 mg Aldafermin, or placebo) and visit. Summaries for continuous endpoints will be provided for the actual value, change and percent change from baseline (if applicable), respectively.

[figure not shown]
## 5.1 Primary Efficacy Analyses

[figure not shown]
## 5.1.1 Primary Efficacy Endpoint

The primary efficacy endpoint for this study is a binary response derived from the liver biopsy assessments of the NAFLD activity score (NAS) and fibrosis score defined by NIH NASH CRN (Appendix A). Liver biopsies are collected at Screening (prior to the study randomization) and Week 24, and will be assessed by a qualified central study pathologist.

The primary efficacy endpoint is the liver fibrosis response at Week 24 (hereafter referred to as "fibrosis response"), defined as a subject achieving an improvement in liver fibrosis greater than or equal to one stage (NASH CRN fibrosis score) with no worsening of steatohepatitis after 24 weeks of treatment. In this definition, fibrosis stages 1a, 1b and 1c are all considered stage 1, and no worsening of steatohepatitis is defined as no increase in NAS for ballooning, inflammation, or steatosis.

## 5.1.2 Primary Estimand

# 5.1.3 Statistical Hypotheses

The statistical hypotheses (null and alternative) to be tested with respect to the fibrosis response are:

[figure not shown]
- H0 (Null Hypothesis): there is no dose-response relationship between Aldafermin dose and the fibrosis response.
- H1 (Alternative Hypothesis): there is a dose-response relationship between Aldafermin dose and the fibrosis response.

These hypotheses will be tested using the MCP-Mod (multiple comparison procedure - modelling) approach proposed by Klingenberg (2009). The details of this approach are provided in Section 5.1.3.

## 5.1.4 The MCP-Mod Approach

[figure not shown]
The MCP-Mod approach is a two-stage procedure in which a set of plausible dose-response models are selected at the design stage. These candidate models will then be used for both dose-response testing (MCP step) and estimation (Mod step) at the analysis stage. The dose-response testing will be performed using an appropriate multiple comparison method to account for the multiplicity issue associated with the multiple candidate models.

This section provides the statistical details of the MCP-Mod approach to be used in the data analysis for this study. The SAS implementation of this approach is provided in Appendix B.

Page 17 of 36

# 5.1.5 Data Analyses

For the primary efficacy analyses, missing fibrosis responses will be imputed using a multiple imputation (MI) method under the assumption of missing at random (MAR). The MI inference involves the following three distinct steps: imputation, analysis and pooling. The details of these steps are described as follows.

#### **Imputation**

Missing fibrosis responses are imputed 25 times to generate 25 complete data sets. The imputed values will be obtained using a logistic model with fixed effects for treatment group and baseline fibrosis stage. At the end of this step, all the 25 complete data sets contain the same non-missing values while the missing values are replaced by imputed values. The following is an example of SAS programming code to be implemented.

The random seeds to be used for this and all subsequent analyses are provided in Appendix C.

#### Analysis

Each of the 25 competed data sets will be analyzed using the MCP-Mod approach described in Section 5.1.3. The SAS programming code to be implemented for this approach is provided in Appendix B. Results to be obtained from each data set include the multiplicity adjusted p-value for each candidate model (macro MCP), the point estimate of the response rate  $\hat{F}(x)$  (E4) for each dose level and the standard error for  $\hat{F}(x)$  (macro Mod). The standard error will be estimated by the sample standard deviation obtained from the bootstrap distribution of the point estimate (E4).

